
 To explore relationships of GSK2857916 plasma concentrations/exposure with pharmacodynamics (PD), safety and clinical activity 	
 Relationship between receptor occupancy, tumor cell death markers, sBCMA and GSK2857916 plasma PK parameters; Relationship between safety/clinical activity (e.g. ORR) and GSK2857916 PK parameters

 To characterize the relationship between clinical response and other biologic tumor characteristics (DNA, protein analysis) 	
 BCMA expression levels on malignant cells as measured by IHC and/or flow cytometry in tumor tissue, serum sBCMA levels and their relationship to clinical response

 To investigate the relationship between genetic variants in the host and response to study medicine, or susceptibility, severity and progression of disease 	
 Relationship between host genetic variation and response to study medicine or susceptibility, severity and progression of disease

Objectives	Endpoints

 To explore the effect of GSK2857916 on symptoms (including bone pain, fatigue and visual symptoms) and impacts on HRQoL in subjects with relapsed/refractory MM (Part 2) 	
 Changes from baseline in bone pain/fatigue and analgesic use as measured by the eDiary Interviews with subjects to further characterize changes in symptoms (including bone pain/, fatigue and visual symptoms) and impacts on HRQoL

 To explore changes in visual symptoms and function following discontinuation of treatment with GSK2857916 	
 Changes in visual symptoms and impacts as measured by the OSDI and NEI-VFQ-25 following treatment discontinuation Follow-up telephone interviews conducted to further understand subjects experience with visual symptoms and changes in symptoms and related impacts following treatment discontinuation

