- If a subject has neither progressed nor died nor started new anti-cancer therapy, then PFS will be censored at the date of the last adequate assessment defined as an assessment where the Investigator determined response is sCR, CR, VGPR, PR, MR or SD. The date of response will be used as the censoring date.

A summary of the assignments for progression and censoring dates for PFS are specified in Table 5.

Table 5 Assignments for Progression and Censoring Dates for PFS Analysis

Situation	Date of Event (Progression/Death) or Censoring	Outcome Event (Progression/Death) Or Censored
No (or inadequate) baseline tumor assessments ^[1] and the subject has not died (if the subject has died follow the rules for death indicted at the bottom of the table)	First dose date	Censored
No post-baseline assessments and the subject has not died (if the subject has died follow the rules for death indicted at the bottom of the table)	First dose date	Censored
Progression documented between scheduled visits	Date of assessment of progression ^[1]	Event
No progression (or death)	Date of last 'adequate' assessment of response ^[2]	Censored
New anticancer treatment started (prior to documented disease progression or death) ^[3] .	Date of last 'adequate' assessment of response ^[2] (on or prior to starting anti-cancer therapy)	Censored
Death before first PD assessment (or Death at baseline or prior to any adequate assessments)	Date of death	Event
Death between adequate assessment visits	Date of death	Event
Death or progression after an extended loss-to-follow-up time (two or more missed cycles + 7 day window) ^[4]	Date of last 'adequate' assessment of response ^[2] (prior to missed assessments)	Censored

[1] **In part 1**, adequate baseline assessment is defined as at baseline, a patient has at least one of the following measurements: a. Serum M-protein or b. Urine M-protein or c. Serum FLC assay or d. Biopsy proven plasmacytoma (should be measured within 28 days of Screening Visit).

In part 2, adequate baseline assessment is defined as at baseline, a patient has at least one of the following measurements: a. Serum M-protein ≥ 0.5 g/dL (≥ 5 g/L) or b. Urine M-protein ≥ 200 mg/24h or c. Serum FLC assay: Involved FLC level ≥ 5 mg/dL (≥ 50 mg/L) and an abnormal serum free light chain ratio (<0.26 or >1.65) or d. Biopsy proven plasmacytoma (should be measured within 28 days of Screening Visit and no later than the first dose date).

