16.7.2. Handling of Missing Data

Element	Reporting Detail
General	
 • Missing data occurs when any requested data is not provided, leading to blank fields on the collection instrument: 
 ○ These data will be indicated by the use of a blank in subject listing displays. Unless all data for a specific visit are missing in which case the data is excluded from the table. ○ Answers such as “Not applicable” and “Not evaluable” are not considered to be missing data and should be displayed as such.
Outliers	
 • Any participants excluded from the summaries and/or statistical analyses will be documented along with the reason for exclusion in the clinical study report.
Responder Analysis	
 • For endpoints which determine the percentage of responders, subjects with unknown/not evaluable or missing best overall response will be assumed to be non-responders, and will be included in the denominator when calculating the percentages.
Time to Event	
 • Because study treatment is dependent on the study endpoints (e.g., progression, i.e. not a fixed treatment duration), the length of treatment for each subject will depend on the efficacy and toxicity of the treatment, so the duration of treatment will vary across subjects. Similarly the duration of follow up will also vary. All available time-to-event data will be analyzed using suitable statistical methods; subjects with shorter treatment and follow-up due to the natural history of their disease or medical necessities of the treatment of their disease will not be considered to have missing time-to-event data.

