TOTAUC	Total AUC (ug.day/mL)		(Total dose received)/Individual Clearance of ADC	popPK output
Q4TOTAUC	Quartile of TOTAUC	0,1,2,3		derived
Q5TOTAUC	Quintile of TOTAUC	0,1,2,3,4		derived
MMAFAUC	First dose AUC(0-inf) of MMAF (ug.day/mL)		First dose (mg)/Individual Clearance of MMAF	popPK output
Q4MMAFAUC	Quartile of MMAFAUC	0,1,2,3		derived
Q5MMAFAUC	Quintile of MMAFAUC	0,1,2,3,4		derived
MMAFTOTAUC	Total AUC (ug.day/mL)		(Total dose received)/Individual Clearance of MMAF	popPK output
Q4MMAFTOTAUC	Quartile of MMAFTOTAUC	0,1,2,3		derived
Q5MMAFTOTAUC	Quintile of MMAFTOTAUC	0,1,2,3,4		derived

For efficacy

Column Header	Data Item	Codes	Derivation/Comments	Source data set
C	Exclusion identifier	Row Number DORDM	Set to line/row number unless one or more of the following conditions are met, then set to code: 
 DORDM: If DORD is missing 	adtte
STUDY	Study ID		1 = BMA117159	adsl
SUBJID	Subject identifier from source data		SUBJID = SUBJID	adsl
ID	NONMEM subject identifier		Sequential subject identifier across studies after data is sorted by SUBJID. Starting with P	derived
PFSCFLCD	PFS Censoring Flag Code	0 or 1	For PARAMCD=PFS_D, CNSR value is assigned to PFSCFLCD 0=Event 1=Censor	adtte
PFSD	PFS (Days)		For PARAMCD=PFS_D, AVAL value is assigned to PFSD	adtte
PFSM	PFS (Months)		For PARAMCD=PFS_M, AVAL value is assigned to PFSM	adtte
PFSY	PFS (Years)		For PARAMCD=PFS_D, (AVAL/365) value is assigned to PFSY	derived
TTRCFLCD	TTR Censoring Flag Code	0 or 1	For PARAMCD=TTR_D, Assign 1 to TTRCFLCD. For subjects where TTR_D is missing, assign 0 to TTRCFLCD.	adtte
TTRD	TTR (Days)		For PARAMCD=TTR_D, AVAL value is assigned to TTRD. For subjects where TTR_D is missing, assign PFSD to TTRD.	adtte
TTRM	TTR (Months)		For PARAMCD=TTR_M, AVAL value is assigned to TTRM. For subjects where TTR_M is missing, assign PFSM to TTRM.	adtte
TTRY	TTR (Years)		For PARAMCD=TTR_D, (AVAL/365) value is assigned to TTRY. For subjects where TTR_D is missing, assign PFSY to TTRY.	derived
DORCFLCD	DOR Censoring Flag Code	0 or 1	For PARAMCD=DOR_D, CNSR value is assigned to DORCFLCD 0=Event 1=Censor Assign "." for missing.	adtte
DORD	DOR (Days)		For PARAMCD=DOR_D, AVAL value is assigned to DORD. For subjects where DOR_D is missing, assign "."	adtte

Column Header	Data Item	Codes	Derivation/Comments	Source data set
DORM	DOR (Months)		For PARAMCD=DOR_M, AVAL value is assigned to DORM. For subjects where DOR_M is missing, assign “.”	adtte

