16.10.2.2.2. Clinical Response

Presence or absence of clinical response will be described using a conventional logistic regression model. Time to response will be explored using Kaplan Meier plots with exposure subdivided into quartiles and quintiles.

PFS will be explored using Kaplan Meier plots with exposure subdivided into quartiles and quintiles and occurrence of progression may also be described using a conventional logistic regression model.

Duration of response will be explored using Kaplan Meier plots with exposure subdivided into quartiles and quintiles.

Best clinical response will be analyzed using an ordered logistic regression, with response categorized from 0 (progressive disease) to 6 (stringent complete response). Exposure will be treated as a categorical variable subdivided into quartiles and quintiles.

In the ordered logistic regression analyses, the use of categorical measures of exposure in lieu of continuous variables will allow for non-parametric descriptions of response functions.

Best clinical response as assessed by maximum reduction in M-protein or FLC will be analyzed by exposure (continuous and/or by quartile and quintile of exposure).

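### The only regression named for progression against exposure is an optional yes/no logistic model with no time horizon; a Cox or parametric survival model on the same dataset would allow for unequal follow-up

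*SAP*

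**What the plan says.** SAP section 16.10.2.2.2 (Clinical Response) commits to a graphical analysis: "PFS will be explored using Kaplan Meier plots with exposure subdivided into quartiles and quintiles". The same sentence continues with an option: "occurrence of progression may also be described using a conventional logistic regression model". No Cox, parametric survival or other time-to-event regression is named for PFS. The section does not say how the logistic outcome is coded for subjects who were censored or who died without progression, and it gives no time by which progression is judged.

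The efficacy dataset in section 16.10.1 holds the time ("For PARAMCD=PFS_D, AVAL value is assigned to PFSD") and one status flag ("For PARAMCD=PFS_D, CNSR value is assigned to PFSCFLCD 0=Event 1=Censor").

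On follow-up, section 16.7.2 states: "Similarly the duration of follow up will also vary". It adds: "All available time-to-event data will be analyzed using suitable statistical methods".

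Section 2.2 lists the matching objective as exploratory: "To explore relationships of GSK2857916 plasma concentrations/exposure with pharmacodynamics (PD), safety and clinical activity".

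**The concern.** A logistic model of occurrence asks whether progression was seen during whatever follow-up a subject happened to have. The question of interest is whether exposure delays progression. The two coincide only if every subject is followed for the same time, and the SAP says that they are not.

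Under the PFS rules, censoring can come very early. Table 5 in section 7.3.1.2.1 censors a living subject with no post-baseline assessment at the first dose. For a subject without progression, death or new therapy, "then PFS will be censored at the date of the last adequate assessment defined". Section 16.5.4 also censors a documented progression or death that falls more than 49 days after the last adequate assessment. If the PFS flag is the logistic outcome, all of these subjects count as progression-free, including some whose progression is on record. Deaths without progression would count as progression.

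The Kaplan-Meier plots keep time and censoring, but they cut exposure into groups and no effect estimate is specified with them. The yes/no model is therefore the only named route to a quantified exposure-progression relationship.

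**Working it through.** **The plan's own figure.** None exists for this analysis: no hypothesis, alpha, effect size or power is stated. The 89.8% power in section 3.1.2.1.1 belongs to the ORR futility design. It reproduces (type I error 0.0754, power 89.75%, assuming success at 12 or more responses in 40, a Beta(0.2, 0.8) prior and a look after each subject from 15 to 39), but it has no bearing here.

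**Step 1: unequal follow-up alone creates an apparent effect.** With exponential PFS of median m and follow-up u, the chance of an observed event is 1 - 2^(-u/m), so its odds are 2^(u/m) - 1. Assume m = 4 months and the same hazard for everyone.

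- u = 8 months: 2^2 - 1 = 3.00
- u = 11 months: 2^2.75 - 1 = 5.73
- Odds ratio, 8 against 11 months: 3.00 / 5.73 = 0.52
- u = 1 month: 2^0.25 - 1 = 0.19; odds ratio against 11 months: 0.19 / 5.73 = 0.03

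The true hazard ratio is 1 throughout. If shorter follow-up goes with higher exposure, the logistic model reports a protective effect that does not exist.

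**Step 2: power when follow-up is unrelated to exposure.** All inputs are assumed: standard normal exposure, exponential PFS, two-sided 5% likelihood-ratio tests, N of 35, 40 or 73, and a hazard ratio per SD of 0.5 to 0.7. There were 1,000 to 2,000 simulated trials per cell, so the standard error of one power estimate is at most sqrt(0.25/1000) = 1.6 points. For N = 40 and hazard ratio 0.6 per SD, power in %, Cox vs logistic:

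| Events | Equal follow-up | Uniform staggered | Exponential (heavy early) censoring |
|---|---|---|---|
| 40% | 52 vs 52 | 51 vs 47 | 46 vs 35 |
| 60% | 68 vs 64 | 66 vs 56 | 62 vs 33 |
| 80% | 77 vs 63 | 76 vs 54 | 76 vs 26 |
| 90% | 81 vs 55 | 79 vs 42 | 78 vs 16 |

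Points of power lost by logistic regression across all N and hazard ratios run:

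- Equal follow-up: about 0-5 at 40-60% events, 7-16 at 80%, 15-27 at 90%.
- Uniform staggered follow-up (longest five times shortest): about 0-10 at 40-60%, 12-23 at 80%, 22-38 at 90%.
- Exponential censoring: 6-19 at 40%, up to about 70 at 90%.

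**Step 3: false positives when follow-up depends on exposure.** There is no true effect, the nominal level is 5%, and follow-up is multiplied by exp(k × exposure in SD).

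| N | k | Cox | Logistic |
|---|---|---|---|
| 40 | 0 | 5.7% | 5.6% |
| 40 | 0.25 | 5.2% | 22.7% |
| 40 | 0.5 | 5.5% | 59.9% |
| 73 | 0.25 | 5.2% | 35.5% |
| 73 | 0.5 | 5.1% | 84.6% |

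A separate simulation with follow-up falling as exposure rises gave 16-42% for logistic and 4-6% for Cox.

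**Step 4: could follow-up depend on exposure here?** In the Part 2 every-3-weeks myeloma schedule (section 16.2.3.1), the serum and urine myeloma tests are marked at screening and at cycle starts from cycle 2. None is marked at the end-of-treatment visit or in monthly follow-up. Stopping treatment therefore ends these scheduled assessments. Section 16.10.2.2.1 models corneal toxicity against exposure. If higher exposure led to earlier stopping, it would also shorten follow-up for progression. That is an inference, not something the SAP states.

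**The case against.** The strongest reply is that the plan already analyses PFS with a method suited to censoring. The Kaplan-Meier plots are the committed analysis, and they sit in the same sentence as the logistic model, which is only permitted. The promise in section 16.7.2 is therefore not broken. The objective is exploratory, the work is reported separately, and no test is specified. All of this stands, and it keeps the point minor.

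A reader might infer three stronger things that the SAP does not support:

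- **That the plan discards PFS time.** It does not. Only the optional supplement ignores time.
- **That censored subjects are, by rule, scored as progression-free.** No coding rule is written. This is the natural reading because PFSCFLCD is the only PFS status variable in the dataset, but exclusion or a fixed horizon is not ruled out.
- **That the loss is a definite figure, such as up to about 20 points of power.** The SAP gives no event rate, follow-up distribution or effect size for this analysis. Depending on what is assumed, the loss runs from about 0 to about 70 points, so 20 is neither derived from the document nor a maximum.

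The reply does not remove the gap. The plots specify no effect estimate on continuous exposure, and the one regression named does not allow for varying follow-up.

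**Conclusion.** The point holds as a minor improvement to an exploratory analysis. The one regression named for progression against exposure ignores time to event and unequal follow-up, and it leaves the handling of censored subjects unstated.

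If censored subjects are coded as non-progressors, precision is lost. At the assumed settings the loss is close to nil when events are moderate (40-60%) and follow-up is equal, 7 to 23 points of power at 80% events with equal or uniformly staggered follow-up, and larger with heavy early censoring.

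Bias is the more serious consequence. A modest dependence of follow-up on exposure (k = 0.25) took a nominal 5% test to 23% at N = 40, while Cox stayed near 5%. Whether such dependence exists in this trial cannot be told from the SAP. Cox removes this problem only if, at a given exposure, censoring is unrelated to prognosis.

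**What to change.** In section 16.10.2.2.2, replace the logistic option for progression with a Cox (or parametric survival) model of PFS on continuous first-dose exposure (AUC, CMAX, CTAU), using PFSD and PFSCFLCD. Report the hazard ratio per SD or per doubling, with its confidence interval, alongside the Kaplan-Meier plots. First-dose metrics are preferable because the cumulative exposure variables in the dataset run up to the progression date and so carry the outcome time within them.

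If a yes/no model is kept, define progression at a fixed time and state how subjects censored before it, and deaths without progression, are handled.

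The cost is a wording change. Every variable is already specified in section 16.10.1, and no new data are needed.

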16.11. Appendix 11: Abbreviations & Trade Marks

16.11.1. Abbreviations

Abbreviation	Description
ADaM	Analysis Data Model
AE	Adverse Event
AIC	Akaike's Information Criteria
A&R	Analysis and Reporting
CDISC	Clinical Data Interchange Standards Consortium
CI	Confidence Interval
CPMS	Clinical Pharmacology Modelling & Simulation
CS	Clinical Statistics
CSR	Clinical Study Report
CTR	Clinical Trial Register
CV _b / CV _w	Coefficient of Variation (Between) / Coefficient of Variation (Within)
DBF	Database Freeze
DBR	Database Release
BCMA	B cell maturation antigen
BCVA	Best corrected visual acuity
CBR	Clinical benefit rate
CDISC	Clinical Data Interchange Standards Consortium
CI	Confidence interval
CK-MB	Creatine kinase MB-isoenzyme
CL	Clearance
C _{max}	Maximum plasma drug concentration
CPMS	Clinical Pharmacology Modeling and Simulation
CR	Complete response
CRM	Continual Reassessment Method
C _{trough}	Trough plasma concentration
Cys-mcMMAF	cys Monomethyl auristatin F
DLT	Dose limiting toxicity
DOB	Date of Birth
DOR	Duration of response
DP	Decimal Places
eDiary	Electronic Diary
ECOG	Eastern Cooperative Oncology Group
EOI	End of infusion
eCRF	Electronic Case Record Form
EMA	European Medicines Agency
FACTS	Fixed and adapted clinical trials simulator
FDA	Food and Drug Administration
FDAAA	Food and Drug Administration Clinical Results Disclosure Requirements
FLC	Free light chain
FTIH	First time in human
GSK	GlaxoSmithKline

Abbreviation	Description
IA	Interim Analysis
ICH	International Conference on Harmonization
IDMC	Independent Data Monitoring Committee
IDSL	Integrated Data Standards Library
IMMS	International Modules Management System
IP	Investigational Product
ITT	Intent-To-Treat
LDH	Lactate dehydrogenase
MMRM	Mixed Model Repeated Measures
MM	Multiple Myeloma
MMAF	Monomethyl auristatin F
MR	Minimal response
MTD	Maximum Tolerated Dose
NCI-CTCAE	National Cancer Institute – Common Terminology Criteria for Adverse Events
N-CRM	A modification of the Continual Reassessment Method (CRM) proposed by Neuenschwander et al.
NEI-VFQ-25	National Eye Institute Visual Functioning Questionnaire - 25
NONMEM	Non linear mixed effects modelling
ORR	Overall response rate
OS	Overall survival
OSDI	Ocular Surface Disease Index
PCI	Potential Clinical Importance
PD	Pharmacodynamic
PDMP	Protocol Deviation Management Plan
PET	Probability of early termination
PFS	Progression-free survival
PK	Pharmacokinetic
PP	Per Protocol
PR	Partial response
PopPK	Population PK
QC	Quality Control
QoL	Quality of life
QTcF	Frederica's QT Interval Corrected for Heart Rate
QTcB	Bazett's QT Interval Corrected for Heart Rate
RAP	Reporting & Analysis Plan
RAMOS	Randomization & Medication Ordering System
REML	Restricted maximum likelihood
Ro	Observed accumulation ratio
RP2	Recommended Phase 2
SAC	Statistical Analysis Complete
SAE	Serious adverse event
sBCMA	Soluble B-cell maturation antigen
sCR	Stringent complete response
SD	Stable disease
SDSP	Study Data Standardization Plan

Abbreviation	Description
SDTM	Study Data Tabulation Model
SOI	Start of infusion
SPEP	Serum protein electrophoresis
SOP	Standard Operation Procedure
t _{1/2}	Half-life
TA	Therapeutic Area
TFL	Tables, Figures & Listings
Tmax	Time to maximum drug concentration
TTBR	Time to best response
TTP	Time to progression
TTR	Time to response
ULN	Upper limit of normal
UPEP	Urine protein electrophoresis
VGPR	Very good partial response

16.11.2. Trademarks

Trademarks of the GlaxoSmithKline Group of Companies
NONE

Trademarks not owned by the GlaxoSmithKline Group of Companies
FACTS
NONMEM
SAS
WinNonlin

16.12. Appendix 12: List of Data Displays

16.12.1. Data Display Numbering

The following numbering will be applied for RAP generated displays:

Section	Tables	Figures
Study Population	1.0010 to 1.xxxx	11.0010 to 11.xxxx
Efficacy	2.0010 to 2.xxxx	12.0010 to 12.xxxx
Safety	3.0010 to 3.xxxx	13.0010 to 13.xxxx
Pharmacokinetic	4.0010 to 4.xxxx	14.0010 to 14.xxxx
Population Pharmacokinetic (PopPK)	5.0010 to 5.xxxx	15.0010 to 15.xxxx
Pharmacodynamic and / or Biomarker	6.0010 to 6.xxxx	16.0010 to 16.xxxx
Pharmacokinetic / Pharmacodynamic	7.0010 to 7.xxxx	17.0010 to 17.xxxx
Section	Listings	
ICH Listings	1.0010 to 1.xxxx	
Other Listings	30.0010 to 30.xxxx	

16.12.2. Mock Example Shell Referencing

Non IDSL specifications will be referenced as indicated and if required example mock-up displays provided in [Appendix 13](#): Example Mock Shells for Data Displays.

Section	Figure	Table	Listing
Study Population	POP_Fn	POP_Tn	POP_Ln
Efficacy	EFF_Fn	EFF_Tn	EFF_Ln
Safety	SAFE_Fn	SAFE_Tn	SAFE_Ln
Pharmacokinetic	PK_Fn	PK_Tn	PK_Ln
Population Pharmacokinetic (PopPK)	POPPK_Fn	POPPK_Tn	POPPK_Ln
Pharmacodynamic and / or Biomarker	PD_Fn	PD_Tn	PD_Ln
Pharmacokinetic / Pharmacodynamic	PKPD_Fn	PKPD_Tn	PK/PD_Ln

NOTES:

- Non-Standard displays are indicated in the 'IDSL / Example Shell' or 'Programming Notes' column as '[Non-Standard] + Reference.'

16.12.3. Deliverables

Delivery [Priority] ^[1]	Description
DS [X]	During Study
DE [X]	Dose Escalation
IA SAC [X]	Interim Analysis Statistical Analysis Complete
SAC [X]	Final Statistical Analysis Complete

NOTES:

- Indicates priority (i.e. order) in which displays will be generated for the reporting effort.

16.12.4. Study Population Tables

Study Population Tables					
No.	Population	IDSL / Example Shell	Title	Programming Notes	Deliverable [Priority]
Subject Disposition					
1.0010	All Treated	ES8	Summary of Subject Status and Reason for Study Withdrawal (Part 1)	Report for: Part 1, (Summarize: by ascending dose level, Total).	SAC [1]
1.0011	All Treated	ES8	Summary of Subject Status and Reason for Study Withdrawal (Part 2 MM)	Report for: Part 2 MM, (Summarize: only for 3.4 MM).	SAC [A]
1.0012	All Treated	ES8	Summary of Subject Status and Reason for Study Withdrawal (All Treated MM)	Report for: All Treated MM, (Summarize: Total).	SAC [A]
1.0013	All Treated	ES8	Summary of Subject Status and Reason for Study Withdrawal (Part 2 NHL)	Report for: Part 2 NHL, (Summarize: only for 3.4 NHL).	SAC
1.0020	All Treated	SD4	Summary of Treatment Status and Reasons for Discontinuation of Study Treatment (Part 1)	Report for: Part 1, (Summarize: by ascending dose level, Total).	SAC [A]
1.0021	All Treated	SD4	Summary of Treatment Status and Reasons for Discontinuation of Study Treatment (Part 2 MM)	Report for: Part 2 MM, (Summarize: only for 3.4 MM).	SAC [A]
1.0022	All Treated	SD4	Summary of Treatment Status and Reasons for Discontinuation of Study Treatment (All Treated MM)	Report for: All Treated MM, (Summarize: Total).	SAC [A]
1.0023	All Treated	SD4	Summary of Treatment Status and Reasons for Discontinuation of Study Treatment (Part 2 NHL)	Report for: Part 2 NHL, (Summarize: only for 3.4 NHL).	SAC
1.0550	Screened	ES6	Summary of Screening Status and Reasons for Screen Failure (Part 1)		SAC [A]
1.0551	Screened	ES6	Summary of Screening Status and Reasons for Screen Failure (Part 2 MM)		SAC [A]
1.0552	Screened	ES6	Summary of Screening Status and Reasons for Screen Failure (All Treated MM)		SAC [A]

CONFIDENTIAL

BMA117159

Study Population Tables					
No.	Population	IDSL / Example Shell	Title	Programming Notes	Deliverable [Priority]
1.0553	Screened	ES6	Summary of Screening Status and Reasons for Screen Failure (Part 2 NHL)		SAC
1.0030	Enrolled	NS1	Summary of Number of Participant by Country and Site ID (MM)	Include columns: No Treatment, Part 1, Part 2 MM, All Treated MM, Total column will be the subjects enrolled to MM cohort. Add a footnote: This summary is based on all subjects enrolled into multiple myeloma cohorts.	SAC [A]
1.0031	Enrolled	NS1	Summary of Number of Participant by Country and Site ID (NHL)	Include columns: No Treatment, Part 2 NHL, Total column will be the subjects enrolled to NHL cohort. Add a footnote: This summary is based on all subjects enrolled into lymphoma cohorts.	SAC
1.0050	All Treated	IE1	Summary of Inclusion/Exclusion Criteria Deviations (Part 1)	Report for: Part 1, (Summarize: by ascending dose level, Total).	SAC [A]
1.0051	All Treated	IE1	Summary of Inclusion/Exclusion Criteria Deviations (Part 2 MM)	Report for: Part 2 MM, (Summarize: only for 3.4 MM).	SAC [A]
1.0052	All Treated	IE1	Summary of Inclusion/Exclusion Criteria Deviations (All Treated MM)	Report for: All Treated MM, (Summarize: Total).	SAC [A]
1.0053	All Treated	IE1	Summary of Inclusion/Exclusion Criteria Deviations (Part 2 NHL)	Report for: Part 2 NHL, (Summarize: only for 3.4 NHL).	SAC

Study Population Tables					
No.	Population	IDSL / Example Shell	Title	Programming Notes	Deliverable [Priority]
Protocol Deviation					
1.0040	All Treated	DV1	Summary of Important Protocol Deviations (Part 1)	Report for: Part 1, (Summarize: by ascending dose level, Total).	SAC [A]
1.0041	All Treated	DV1	Summary of Important Protocol Deviations (Part 2 MM)	Report for: Part 2 MM, (Summarize: only for 3.4 MM).	SAC [A]
1.0042	All Treated	DV1	Summary of Important Protocol Deviations (All Treated MM)	Report for: All Treated MM, (Summarize: Total).	SAC [A]
1.0043	All Treated	DV1	Summary of Important Protocol Deviations (Part 2 NHL)	Report for: Part 2 NHL, (Summarize: only for 3.4 NHL).	SAC
Population Analysed					
1.0060	Enrolled	SP1	Summary of Study Populations (MM)	Report for: Part 1, (Summarize: by ascending dose level, Total). This table is based on subjects enrolled to MM, we do not have screen failure data, hence no screened population. For columns, include No Treatment, No Treatment for Part 1, No Treatment for Part 2 MM, Dose levels in part 1, All Treated in Part 1, All Treated in Part 2, All Treated and Total. Rows: include Enrolled, Part 1, Part 2 MM, All Treated MM, DLT Evaluable, PK, PD	SAC [A]
1.0061	Enrolled	SP1	Summary of Study Populations (NHL)	Report for: Part 2 MM, (Summarize: only for 3.4 MM). This table is	SAC

Study Population Tables					
No.	Population	IDSL / Example Shell	Title	Programming Notes	Deliverable [Priority]
				based on subjects enrolled to NHL, we do not have screen failure data, hence no screened population. For columns, include No Treatment, All Treated and Total. Rows: include Enrolled, Part 2 NHL, PK, PD	
1.0430	Enrolled	SP2A	Summary of the Exclusions from the Part 1 Population		SAC [A]
1.0431	Enrolled	SP2A	Summary of the Exclusions from the Part 2 MM Population		SAC [A]
1.0432	Enrolled	SP2A	Summary of the Exclusions from the All Treated MM Population		SAC [A]
1.0433	Enrolled	SP2A	Summary of the Exclusions from the Part 2 NHL Population		SAC [A]
1.0434	Enrolled	SP2A	Summary of the Exclusions from the All Treated Population		SAC
1.04354	Enrolled	SP2A	Summary of the Exclusions from the DLT Evaluable Population		SAC [A]
1.0436	Enrolled	SP2A	Summary of the Exclusions from the Pharmacokinetic (PK) Population		SAC [A]
1.0437	Enrolled	SP2A	Summary of the Exclusions from the Pharmacodynamic (PD) Population		SAC [A]
Demographic and Baseline Characteristics					
1.0070	All Treated	DM1	Summary of Demographic Characteristics (Part 1)	Report for: Part 1, (Summarize: by ascending dose level, Total).	SAC [A]
1.0071	All Treated	DM1	Summary of Demographic Characteristics (Part 2 MM)	Report for: Part 2 MM, (Summarize: only for 3.4 MM).	SAC [A]
1.0072	All Treated	DM1	Summary of Demographic Characteristics (All Treated MM)	Report for: All Treated MM, (Summarize: Total).	SAC [A]

CONFIDENTIAL

BMA117159

Study Population Tables					
No.	Population	IDSL / Example Shell	Title	Programming Notes	Deliverable [Priority]
1.0073	All Treated	DM1	Summary of Demographic Characteristics (Part 2 NHL)	Report for: Part 2 NHL, (Summarize: only for 3.4 NHL).	SAC
1.0290	Enrolled	DM11	Summary of Age Ranges (MM)	Include columns "No Treatment", "Part 1", "Part 2 MM", "All Treated MM", "Total"	SAC [1]
1.0291	Enrolled	DM11	Summary of Age Ranges (NHL)	Include columns "No Treatment", "Part 2 NHL", "Total"	SAC
1.0080	All Treated	DM5	Summary of Race and Racial Combinations (Part 1)	Report for: Part 1, (Summarize: by ascending dose level, Total).	SAC [A]
1.0081	All Treated	DM5	Summary of Race and Racial Combinations (Part 2 MM)	Report for: Part 2 MM, (Summarize: only for 3.4 MM).	SAC [A]
1.0082	All Treated	DM5	Summary of Race and Racial Combinations (All Treated MM)	Report for: All Treated MM, (Summarize: Total).	SAC [A]
1.0083	All Treated	DM5	Summary of Race and Racial Combinations (Part 2 NHL)	Report for: Part 2 NHL, (Summarize: only for 3.4 NHL).	SAC
1.0090	All Treated	DM6	Summary of Race and Racial Combination Details (Part 1)	Report for: Part 1, (Summarize: by ascending dose level, Total).	SAC [A]
1.0091	All Treated	DM6	Summary of Race and Racial Combination Details (Part 2 MM)	Report for: Part 2 MM, (Summarize: only for 3.4 MM).	SAC [A]
1.0092	All Treated	DM6	Summary of Race and Racial Combination Details (All Treated MM)	Report for: All Treated MM, (Summarize: Total).	SAC [A]
1.0093	All Treated	DM6	Summary of Race and Racial Combination Details (Part 2 NHL)	Report for: Part 2 NHL, (Summarize: only for 3.4 NHL).	SAC

CONFIDENTIAL

BMA117159

Study Population Tables					
No.	Population	IDSL / Example Shell	Title	Programming Notes	Deliverable [Priority]
Prior and Concomitant Medications					
1.0190	All Treated	MH1	Summary of Past Medical Conditions (Part 1)	Report for: Part 1, (Summarize: by ascending dose level, Total).	SAC [A]
1.0191	All Treated	MH1	Summary of Past Medical Conditions (Part 2 MM)	Report for: Part 2 MM, (Summarize: only for 3.4 MM).	SAC [A]
1.0192	All Treated	MH1	Summary of Past Medical Conditions (All Treated MM)	Report for: All Treated MM, (Summarize: Total).	SAC [A]
1.0193	All Treated	MH1	Summary of Past Medical Conditions (Part 2 NHL)	Report for: Part 2 NHL, (Summarize: only for 3.4 NHL).	SAC
1.0200	All Treated	MH1	Summary of Current Medical Conditions (Part 1)	Report for: Part 1, (Summarize: by ascending dose level, Total).	SAC [A]
1.0201	All Treated	MH1	Summary of Current Medical Conditions (Part 2 MM)	Report for: Part 2 MM, (Summarize: only for 3.4 MM).	SAC [A]
1.0202	All Treated	MH1	Summary of Current Medical Conditions (All Treated MM)	Report for: All Treated MM, (Summarize: Total).	SAC [A]
1.0203	All Treated	MH1	Summary of Current Medical Conditions (Part 2 NHL)	Report for: Part 2 NHL, (Summarize: only for 3.4 NHL).	SAC
1.0210	All Treated	CM8	Summary of Concomitant Medications (Part 1)	Report for: Part 1, (Summarize: by ascending dose level, Total).	SAC [A]
1.0211	All Treated	CM8	Summary of Concomitant Medications (Part 2 MM)	Report for: Part 2 MM, (Summarize: only for 3.4 MM).	SAC [A]
1.0212	All Treated	CM8	Summary of Concomitant Medications (All Treated MM)	Report for: All Treated MM, (Summarize: Total).	SAC [A]
1.0213	All Treated	CM8	Summary of Concomitant Medications (Part 2 NHL)	Report for: Part 2 NHL,	SAC

Study Population Tables					
No.	Population	IDSL / Example Shell	Title	Programming Notes	Deliverable [Priority]
				(Summarize: only for 3.4 NHL).	
1.0380	All Treated	CM1	Summary of Prophylactic Medication for Infusion-Related Reactions by Drug Class and Drug Name (Part 1)	Report for: Part 1, (Summarize: by ascending dose level, Total). Please replace ATC Level 1 by 'Drug Class' and 'Ingredient' by 'Drug'. Replace the footnote as "Subjects may be included in more than one category for 'Drug Class' and 'Drug'.	SAC [A]
1.0381	All Treated	CM1	Summary of Prophylactic Medication for Infusion-Related Reactions by Drug Class and Drug Name (Part 2 MM)	Report for: Part 2 MM, (Summarize: only for 3.4 MM). Please replace ATC Level 1 by 'Drug Class' and 'Ingredient' by 'Drug'. Replace the footnote as "Subjects may be included in more than one category for 'Drug Class' and 'Drug'.	SAC [A]
1.0382	All Treated	CM1	Summary of Prophylactic Medication for Infusion-Related Reactions by Drug Class and Drug Name (All Treated MM)	Report for: All Treated MM, (Summarize: Total). Please replace ATC Level 1 by 'Drug Class' and 'Ingredient' by 'Drug'. Replace the footnote as "Subjects may be included in more than one category for 'Drug Class' and 'Drug'.	SAC [A]
1.0383	All Treated	CM1	Summary of Prophylactic Medication for Infusion-Related Reactions by Drug Class and Drug Name (Part 2 NHL)	Report for: Part 2 NHL, (Summarize: only for 3.4 NHL). Please replace ATC Level 1 by 'Drug Class' and 'Ingredient' by 'Drug'. Replace the footnote as "Subjects may be included in more	SAC

Study Population Tables					
No.	Population	IDSL / Example Shell	Title	Programming Notes	Deliverable [Priority]
				than one category for 'Drug Class' and 'Drug'.	
1.0510	All Treated	OSP2	Summary of Prior Cancer and Non-Cancer Related Surgical Procedures (Part 1)	Report for: Part 1, (Summarize: by ascending dose level, Total). If the CRF does not have any coded procedures and collection of surgeries is restricted to prior cancer related surgeries, then a summary is not necessary as the number and percent of subjects with surgeries will be provided in the anticancer therapy display (see Example AC1). Otherwise a simplified version of the summary can be utilized if appropriate (see example OSP2).	SAC [A]
1.0511	All Treated	OSP2	Summary of Prior Cancer and Non-Cancer Related Surgical Procedures (Part 2 MM)	Report for: Part 2 MM, (Summarize: only for 3.4 MM).	SAC [A]
1.0512	All Treated	OSP2	Summary of Prior Cancer and Non-Cancer Related Surgical Procedures (All Treated MM)	Report for: All Treated MM, (Summarize: Total).	SAC [A]
1.0513	All Treated	OSP2	Summary of Prior Cancer and Non-Cancer Related Surgical Procedures (Part 2 NHL)	Report for: Part 2 NHL, (Summarize: only for 3.4 NHL).	SAC
Exposure and Treatment Compliance					
1.0240	All Treated	OEX5	Summary of Exposure to GSK2857916 (Part 1)	Report for population: Part 1, (Summarize: by ascending dose level, Total). Do not need "Dose Intensity "	SAC [A]

CONFIDENTIAL

BMA117159

Study Population Tables					
No.	Population	IDSL / Example Shell	Title	Programming Notes	Deliverable [Priority]
				section. Use 4, <4, >4 cycles	
1.0241	All Treated	OEX5	Summary of Exposure to GSK2857916 (Part 2 MM)	Report for population: Part 2 MM, (Summarize: only for 3.4 MM). Do not need "Dose Intensity " section. Use 4, <4, >4 cycles	SAC [A]
1.0242	All Treated	OEX5	Summary of Exposure to GSK2857916 (All Treated MM)	Report for population: All Treated MM, (Summarize: Total) Do not need "Dose Intensity " section. Use 4, <4, >4 cycles	SAC [A]
1.0243	All Treated	OEX5	Summary of Exposure to GSK2857916 (Part 2 NHL)	Report for population: 3.4 NHL, (Summarize: Total) Do not need "Dose Intensity " section. Use 4, <4, >4 cycles	SAC
1.0230	All Treated	OEX6	Summary of Dose Intensity of GSK2857916 by Cycle (Part 1)	Report for: Part 1, (Summarize: by ascending dose level, Total). Dose Intensity(mg/kg/cycle)	SAC [A]
1.0231	All Treated	OEX6	Summary of Dose Intensity of GSK2857916 by Cycle (Part 2 MM)	Report for: Part 2 MM, (Summarize: only for 3.4 MM). Dose Intensity(mg/kg/cycle)	SAC [A]
1.0232	All Treated	OEX6	Summary of Dose Intensity of GSK2857916 by Cycle (All Treated MM)	Report for: All Treated MM, (Summarize: Total). Dose Intensity(mg/kg/cycle)	SAC [A]
1.0233	All Treated	OEX6	Summary of Dose Intensity of GSK2857916 by Cycle (Part 2 NHL)	Report for: Part 2 NHL, (Summarize: only for 3.4 NHL). Dose Intensity(mg/kg/cycle)	SAC

CONFIDENTIAL

BMA117159

Study Population Tables					
No.	Population	IDSL / Example Shell	Title	Programming Notes	Deliverable [Priority]
1.0250	All Treated	ODMOD 1	Summary of Dose Reductions of GSK2857916 (Part 1)	Report for: Part 1, (Summarize: by ascending dose level, Total).	SAC [A]
1.0251	All Treated	ODMOD 1	Summary of Dose Reductions of GSK2857916 (Part 2 MM)	Report for: Part 2 MM, (Summarize: only for 3.4 MM).	SAC [A]
1.0252	All Treated	ODMOD 1	Summary of Dose Reductions of GSK2857916 (All Treated MM)	Report for: All Treated MM, (Summarize: Total).	SAC [A]
